### 5.5 Deviation from Inclusion/Exclusion Criteria

This study is intended to be conducted as described in this protocol. Waivers from inclusion and exclusion criteria are not allowed because they have the potential to jeopardize subject safety, the scientific integrity of the study or regulatory acceptability of the data. Indivior does not grant waivers to the protocol-defined inclusion and exclusion criteria, and strict adherence to these criteria as outlined in the protocol is essential. The Principal Investigator (PI), sub-Investigator or suitably qualified designee will be responsible for identifying, documenting and reporting all deviations, which are defined as isolated occurrences involving a procedure that did not follow the study protocol or study-specific procedure. In the event of a major deviation from the protocol due to an emergency, accident or mistake (e. g., eligibility or dosing errors), the PI, sub-Investigator or suitably qualified designee must contact the Indivior Medical Monitor at the earliest possible time by telephone. This will allow an early joint decision regarding the subject's continuation in the study. This decision will be documented by the Investigator and the Sponsor. Deviations will be reported as required to the Institutional Review Board (IRB) per their reporting process and criteria, and in the final study report.

Protocol deviations will be identified and documented through programmatic checks of study data, as well as through review of selected subject data listings prior to database lock.

## 6 STUDY CONDUCT

#### 6.1 Subject Enrollment

Study participation begins once written informed consent is obtained; a subject identification (ID) is then randomly assigned. The subject ID will be used to identify the subject during the screening process and throughout study participation, if applicable.

The Investigator is responsible for maintaining a master list (i.e., a subject ID list) of all consented subjects .This document will be reviewed by Indivior or designated representative for accuracy and completeness. Ineligible subjects, as defined by the protocol-specific inclusion and exclusion criteria, should not receive IMP and should be documented as screen failures.

#### 6.2 Screen Failure

A subject will be considered a screen failure if written informed consent is obtained but the subject did not meet inclusion or exclusion criteria. The study site will keep a Screening Log documenting subjects who have signed an informed consent. Screen failure reasons will be documented on the Screening Log as well as collected in the electronic case report form (eCRF).

#### 6.3 Subject Completion

A completed subject is one that has completed the EOS visit. The end of the study is defined as the last subject's last visit.

### 6.4 Dose Escalation and Stopping Criteria

### 6.4.1 Dose Escalation Criteria

Data Review and Safety Committee (DRSC, See Section 15.2) will review data from cohorts, and will determine if the dose can be escalated, or alternatively if any stopping criteria have been met.

#### **Stopping Criteria**

The study will be paused pending evaluation of all available data by the DRSC, if any of the criteria listed below are fulfilled for an individual dosing cohort:

#### AEs:

#### Laboratory Abnormalities:

#### Vital Signs:

#### ECG Criteria:

#### 6.5 Subject Withdrawal from the Study

If the subject has permanently discontinued study treatment and is no longer being followed for study assessments and procedures (including follow-up procedures), he/she will be considered withdrawn from the study. The primary reason for withdrawing from the study must be entered into the eCRF (e.g., subject is lost to follow-up, Indivior terminates the study or Investigator discretion).

If a subject wishes to leave the study at any time, they will be permitted to do so. Every reasonable effort will be made to complete the Early Termination (ET) assessments and procedures. The primary reason for withdrawing from the study must be entered into the eCRF (e. g., subject is lost to follow-up, Indivior terminates the study or Investigator discretion). For any subject who withdraws from the study, every effort will be made to ensure the subject completes EOS/ET procedures.

For a subject who discontinues due to an AE, see Section 10.1.1 for follow-up procedures. Any subject withdrawn or discontinuing the study after being dosed will not be replaced.

Subjects can be withdrawn from the study for the following reasons:

- Pregnancy
- Termination of the study
- Upon the subject's request (withdrawal of consent)
- Significant deviation from the protocol
- Concurrent illness or requirement for prohibited medication
- At the discretion of the Investigator

#### 6.5.1 Subject Withdrawal of Consent

If a subject withdraws consent, the subject will not receive any additional doses of study drug in Part II. However, the subject may be offered additional tests as needed to monitor their safety (e.g., EOS safety assessments or procedures).

#### 6.5.2 Subjects Lost to Follow-up

In cases of a missed visit, the Investigator or designee must attempt to contact the subject and reschedule as soon as possible. The Investigator or designee must counsel the subject on the importance of maintaining the assigned visit schedule and ascertain whether or not the subject wishes to and/or should continue in the study.

In the event a subject is lost to follow-up, the Investigator or designee must make a reasonable effort to contact the subject. Two documented attempts (e. g., phone, email, etc.) to contact the subject followed by a certified mailed letter is considered reasonable.

For the purpose of documenting date of discontinuation for a subject confirmed to be lost to follow-up, the date of discontinuation should be the date of last contact with the subject.

- In the case where a certified letter is sent but not confirmed as received by the subject, the date of discontinuation is the date the certified letter was sent.
- In the case where a certified letter is sent and has been confirmed as received by the subject, the date of discontinuation is the date of the confirmed subject receipt.
- In the event that neither of these above cases applies (which should be explained in the source documents), the date of discontinuation is the date of the subject's last study visit.

## 7 STUDY SUSPENSION OR TERMINATION

Indivior reserves the right to temporarily suspend and/or permanently discontinue the study at any time and for any reason, including safety or ethical concerns or severe noncompliance. If such action is taken, Indivior will discuss the rationale for the decision with the PI. In cases where a study is suspended or terminated for safety reasons, Indivior will promptly inform Investigators and the Regulatory Authorities of this action and the reason(s) for the suspension or termination.

If required by applicable regulations, the Investigator must inform the IRB promptly and provide the reason(s) for the suspension or termination. If the study is prematurely discontinued, all study data and drug substance remaining on-site will be returned to Indivior or its designated representative.

## 8 DESCRIPTION OF STUDY PROCEDURES

Study assessments and procedures, including the timing of assessments, are summarized in Schedule of Events tables for Part I and Part II (Section 22.1, Appendix 1 and Section 22.2, Appendix 2). Further details on safety and PK assessments are provided in Section 14.7 and Section 14.4, respectively.

See Section 0 for description of AE procedures.

#### 8.1 Informed Consent

A signed written ICF (Informed Consent Form) must be obtained from the subject or a legal representative before any study assessments or procedures may be performed. The potential subject will be given the IRB-approved ICF to review and will have the opportunity to ask questions concerning the study until he or she is satisfied. The potential subject should be able to answer simple questions about the study after the ICF has been reviewed and explained. After this explanation, the potential subject will be asked to sign and date the written ICF. The PI or designee obtaining informed consent from the subject will also sign the ICF to confirm that consent has been obtained as required. A copy of the signed ICF will be given to the subject.

#### 8.2 Demographics and Medical History

The following demographic information will be captured: sex, race, date of birth, ethnicity, height, weight and BMI.

A detailed medical history will be obtained during the screening period. This will include information regarding the subject's complete history of relevant medical conditions, diagnoses, procedures, treatments and any other noteworthy medical information. Any updates to medical history information made available during the course of the study will be captured.

### 8.3 Physical Examination

At Screening, a complete physical examination will include an assessment of general appearance, skin and extremities, head and neck, lymph nodes, eyes, ears, nose, throat, thyroid, neurological system, lungs, cardiovascular system, and abdomen (liver and spleen). The physical exam will not include a breast, pelvic or rectal examination unless clinically indicated.

#### After the screening period, brief physical examinations will occur

Any clinically significant abnormalities, including changes from baseline, must be reported as AEs.

### 8.4 Body Weight

The subject's body weight will be measured as detailed in Section 22.1 Appendix 1 and Section 22.2 Appendix 2.

### 8.5 Vital Signs

Blood pressure, heart rate, respiratory rate and temperature will be measured by automated recorders after the subject has been in a semi-recumbent position for a minimum of 3 min according to the time schedule presented in the Schedule of Events tables (Section 22.1, Appendix 1 and Section 22.2, Appendix 2). The mean of the triplicate measures of blood pressure will define baseline SBP and DBP at the pre-dose timepoint.

If a subject shows an abnormal assessment at any stage, repeat measurements may be made, and the abnormality followed to resolution if required. Additional measurements may be taken as deemed necessary by the Investigator.

Any clinically significant abnormalities, including changes from baseline, must be reported as AEs.

### 8.6 12-Lead Electrocardiograms

A 12-lead ECG will be recorded after the subject has been in the semi-recumbent position for a minimum of 5 minutes as presented in the Schedule of Events tables (Section 22.1. Appendix 1 and Section 22.2, Appendix 2).

A triplicate ECG will be recorded for the determination of the baseline result at pre-dose. The baseline value will be the mean of the 3 recordings. If a potentially clinically significant abnormality is noted during other ECG assessments, a triplicate ECG will be taken at that timepoint. All triplicate ECG recordings should occur at least 1 minute apart. If a subject shows an abnormal assessment at any stage, repeat measurements may be made and the abnormality followed to resolution, if required. Additional measurements may be taken as deemed necessary by the Investigator.

Any clinically significant abnormalities, including changes from baseline, will be reported as AEs.

## 8.7 26 Hour Holter Monitoring

Continuous 12-lead ECG tracings will be recorded on Day 1 from at least 2 hours pre-dose until at least 24 hours post-dose.

Subjects should be semi-recumbent for at least 10 minutes prior to the following time points: Part 1: At 3 time points prior to dosing, e.g., -45, -30 and -15 minutes, and then at 0.5, 1, 2, 3, 4, 6, 8, 12 hours post-dose; Day 2 (24 hours post-dose). Part II: At 3 time points prior to dosing, Confidential Page 33 of 89 e.g., -45, -30 and -15 minutes, and then at 0.5, 1, 2, 3, 4, 6, 8, 12 hours post-dose; Day 2 (24 hours post-dose). All extractions should occur within  $\pm$  15 minutes of the nominal PK timepoint. At time points with multiple activities, the preferred order of events is as follows: Holter extraction, safety ECG, vitals, PK collection. The PK collection takes precedence for being scheduled at the nominal time point.

#### 8.9 Clinical Laboratory Tests

Clinical laboratory tests will be performed at the time points listed in Section 22.1 and Section 22.2 in a licensed clinical laboratory. A serum pregnancy test will be conducted at screening, while all remaining pregnancy tests will be urine pregnancy tests performed using a licensed test (dipstick). Subjects are to be in a seated or semi-recumbent position during blood collection.

The following clinical laboratory tests (Table 1) will be performed according to the Schedule of Events tables in Section 22.1, Appendix 1 and Section 22.2, Appendix 2:

Hematology	Serum Chemistry:
Hematocrit	Albumin
Hemoglobin	Alkaline phosphatase
Mean corpuscular hemoglobin	Alanine aminotransferase (ALT)
Mean corpuscular hemoglobin concentration	Amylase
Mean corpuscular volume	Aspartate aminotransferase (AST)
Platelet count	Blood urea nitrogen
Red blood cell count	Calcium
White blood cell count with differential (absolute	Carbon dioxide
count)	Chloride
	Creatinine
Urinalysis:	Creatine kinase
Appearance	Gamma-glutamyl transferase
Bilirubin	Glucose (non-fasting)
Color	Lactate dehydrogenase
Glucose	Lipase
Ketones	Magnesium
Leucocyte esterase	Phosphorus

### Table 1 List of Laboratory Tests

Confidential

Microscopic examination of sediment a	Potassium
Nitrite	Sodium
Occult blood	Total bilirubin
pH	Direct bilirubin
Protein	Total cholesterol
Specific gravity	Total protein
Urobilinogen	Triglycerides
Hormone Panel:	Urine Drug Screen (UDS):
Follicle Stimulating Hormone	Opioids
	Cocaine
Pregnancy:	Amphetamines
Serum hCG	Cannabinoids
	Barbiturates
Screening Only:	Benzodiazepines
Hemoglobin A1c	Methamphetamine
Hepatitis B surface Antigen	Phencyclidine
Hepatitis C Antibody	Ethanol
HIV-1 and -2 antibodies	
Prothombin Time (PT) with INR	
PTT	

Anti-HIV = human immunodeficiency virus antibodies; hCG = human chorionic gonadotropin; INR = international normalized ratio; PT = prothrombin time; and PTT = partial thromboplastin time.

a Microscopic examination of sediment will be performed only if the results of the urinalysis evaluation are positive (microscopic examination may include but is not limited to White Blood Cell count, Red Blood Cell count, casts and crystals).

## 8.9.1 Sample Collection, Storage and Shipping

Details for the collection, preparation, storage and shipment of centrally tested laboratory specimens will be outlined in the laboratory manual(s).

## 8.10 Pharmacokinetic Assessments

## 8.10.1 Plasma Samples for Pharmacokinetic Analysis

Blood samples for PK analysis of INDV-2000 metabolite metabolite will be collected at the time points listed in Section 22.4, Appendix 4. Depending on PK results from the first dose levels, up to 2 additional samples may be added or the schedule of samples may be modified. Approximately 14 blood samples of 6 mL per sample for PK in total will be taken from any subject, however, it could be more if the subject experiences an SAE, or requires their
sample(s) retaken. The actual date and time of each sample collection will be documented. Samples will be collected into appropriate tubes as specified by the bioanalytical laboratory. Details of sample tubes, processing, storage and shipping procedures are provided in the Laboratory Manual.

Additional PK samples may be collected for subjects who experience a SAE. Samples should be collected as soon as the Investigator is made aware of the SAE and additional blood samples may be collected, after a period of time, to confirm resolution of the SAE.

## 8.10.3 Sample Analysis

Concentrations of INDV-2000 and in plasma validated bioanalytical methodology.

will be determined using the

## 8.11 Appropriateness of Measurements

The clinical data measures to be employed in this study are standard, generally accepted measures used for decision-making in clinical practice.

The conventional safety assessments that will be used in this study are suitable, standard and widely used measures for evaluating the safety of the study drug. Measurement of drug levels in plasma power time is a standard evaluation of PK parameters.

## 8.12 Protocol Deviations

A protocol deviation is any noncompliance with the clinical study protocol or ICH/GCP requirements. The noncompliance may be either on the part of the subject, the Investigator or the study site staff. As a result of deviations, corrective actions are to be developed by the site and implemented promptly and in accordance with ICH E6 Good Clinical Practice guidelines. It is the responsibility of the Investigator and study site staff to use continuous vigilance to identify and report deviations to Indivior or specified designee and the IRB per the IRB's reporting requirements. The Investigator and study site staff are responsible for knowing and adhering to

the IRB's requirements. Protocol deviations must be documented and will be included in the final study report.

#### 8.13 Order of Procedures

Acceptable windows for assessment timepoints are located in the footnotes of the Schedule of Events tables, Section 22.1 Appendix 1 and Section 22.2 Appendix 2.

It is recommended that on days/times with multiple assessments, the assessments are completed in the following order, when applicable.

- ECG
- Vital signs
- Plasma PK
- PD assessments as applicable to Part I

## 9 STUDY DRUG MANAGEMENT

#### 9.1 Description

INDV-2000 is intended for oral administration and will be dosed as either a powder in solution

or a powder in

capsule

Indivior will provide drug substance to the clinic pharmacy and the required dosages and matching placebos will be prepared by the study site per site procedures in compliance with USP <795>, Pharmaceutical Compounding- Nonsterile Preparations and the Pharmacy Manual.

The term 'study drug' describes both drug product and placebo and is received by the subject as per the protocol design.

#### 9.1.1 Drug Substance Manufacturer

Drug substance is manufactured in accordance with current Good Manufacturing Practices (GMP) at the following facility:

#### 9.1.2 Placebo

Placebo formulations will be prepared by the study site to visually match each of the required study drug dosages.

## 9.1.3 Blinding and Randomization

Part I of this study will be double-blinded to include the subjects, the Investigator and the Sponsor

Active drug assignment will not be known to the subjects, the clinical site staff who are involved in the clinical evaluation of the subjects and the analysis of data or the dosing team. The randomization schedule and disclosure envelopes will be generated by an unblinded statistician. The unblinded statistician will not be involved in any decisions relating to populations for analysis prior to unblinding. Prior to database lock and unblinding, all randomization materials, including the final signed and dated randomization schedule, will be held by the pharmacy department of the clinical site.

Interim PK parameter estimations will be performed using bioanalytical data applied with subject aliases in order to maintain the study blind. Interim PK analysis will be performed using nominal time points.

The unblinded pharmacist or designee at the clinical site will receive a copy of the final randomization schedule for preparation of the IMP and preparation of the treatment allocation list. A copy of the randomization schedule will also be made available to the laboratory performing the bioanalysis to allow selective analysis of PK samples to obtain drug concentrations.

One set of disclosure envelopes (i.e., sealed envelopes containing individual subject randomization details) will be provided. This set will be held in a secure and locked cabinet in a temporary drug room, having key fob controlled access, located just outside the pharmacy. Disclosure envelopes may be used by the Investigator in the event of an emergency, or if the Investigator deems it necessary to break the study blind in the interest of a subject's medical safety, or if warranted during scheduled safety reviews. Any request for information on the randomization schedule after initial issue must be made using a randomization disclosure form, except in the case of emergency unblinding. The Medical Monitor must be contacted within 24 hr following disclosure of IMP assignment.

Details of any disclosure of the randomization schedule will be documented and retained in the investigator site file (ISF). The Sponsor will be notified if the study blind is broken.

If any blinded study team member suspects that they have been unblinded, they are to immediately notify the Indivior unblinded contact. The suspected unblinded information should not be forwarded or revealed to any other blinded team members.

The study blind will be broken after the study database has been locked.

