### 10.1.3 Assessment of Causality

The Investigator or a medically qualified sub-Investigator, trained on this study protocol and listed on the delegation of authority log is responsible for determining the AE relationship to the IMP.

The following categories will be used to define the relationship of an AE to the administration of the IMP:

Not Related:	Data are available to identify a clear alternative cause for the AE other than the IMP.
Related:	The cause of the AE is related to the IMP and cannot be reasonably explained by other factors (e.g., the subject's clinical state, concomitant therapy and/or other interventions).

A "reasonable possibility" is meant to convey that there are facts/evidence or arguments to suggest a causal relationship, rather than a relationship cannot be ruled out. The Investigator will use clinical judgment to determine the relationship. Alternative causes, such as natural history of the underlying diseases, concomitant therapy, other risk factors and the temporal relationship of the event to the IMP will be considered and investigated. The Investigator will also consult the

IB in the determination of his/her assessment. For each AE/SAE the Investigator must document in the medical notes that he/she has reviewed the AE/SAE and has provided an assessment of causality.

There may be situations when an SAE has occurred, and the Investigator has minimal information to include in the initial report to Indivior or designated representative. However, it is imperative that the Investigator always make an assessment of causality for every event prior to the initial transmission of the SAE data to Indivior or designated representative. The Investigator may change his/her opinion of causality in light of follow-up information and amend the SAE data collection tool accordingly. The causality assessment is one of the criteria used when determining regulatory reporting requirements.

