## 15.2 Data Review and Safety Committee

The DRSC will include the Investigator, Sponsor Medical Monitor and PK scientist. Other members will be added as necessary. The DRSC will be blinded and will review clinical safety, laboratory data and PK data. Based on the data presented, the DRSC may choose to unblind the data to the Sponsor only. Every effort will be maintained to keep the Investigator blinded. The proposed dose escalation scheme for Part I is described in the study design section, however, a more conservative dose escalation may be explored based on PK, safety and/or clinical observations. Dose escalation factors will be dependent upon observed safety, tolerability and PK.

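### In Part I, Protocol 9.1.3 lets the Investigator open disclosure envelopes at scheduled safety reviews, which conflicts with the Sponsor-only unblinding in 15.2 and, if used, could bias the severity and causality parts of the primary endpoint

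*Protocol*

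**What the plan says.** Protocol 9.1.3 sets the blind: "Part I of this study will be double-blinded to include the subjects, the Investigator and the Sponsor". It then says "Disclosure envelopes may be used by the Investigator in the event of an emergency", and adds two further occasions: "in the interest of a subject's medical safety, or if warranted during scheduled safety reviews". The third is tied neither to an emergency nor to the safety of a particular subject.

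Protocol 15.2 deals with unblinding at committee review. On membership: "The DRSC will include the Investigator, Sponsor Medical Monitor and PK scientist". It describes the committee as blinded and says that "the DRSC may choose to unblind the data to the Sponsor only. Every effort will be maintained to keep the Investigator blinded".

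Protocol 14.5 connects the two sections. It names two kinds of Part I review, one of the sentinel data and one of each cohort before escalation, and assigns the safety data review to the DRSC with a reference to 15.2. Protocol 4.1 also points to 15.2 for the sentinel review.

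On assessment, Protocol 10.1 makes the Investigator ultimately responsible for AEs and allows delegation to a medically qualified sub-Investigator. Under 10.1.3 the Investigator or such a sub-Investigator "is responsible for determining the AE relationship to the IMP". Protocol 14.4.1 and SAP Table 1 define the primary endpoint as the incidence, seriousness, severity and relationship to IMP of TEAEs.

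The legible text of SAP 3.4 only restates the double blind, and SAP section 10 gives no unblinding route. The SAP as it can be read does not settle the matter.

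**The concern.** Two sections govern the same meeting and send the allocation to different people. Under 9.1.3 the Investigator opens the envelope, and the Medical Monitor and Sponsor are told that this has happened. Under 15.2 the Sponsor alone may learn the allocation. A site could follow 9.1.3 in good faith at a sentinel or escalation review and so defeat the aim of 15.2.

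What is at stake is blinded judgement of AEs. Severity and relationship are ratings, made by or under the responsibility of the person who would hold the envelope. A rater who knows a subject had active drug may be readier to call an event related, and one who knows a subject had placebo may be less so. Part II is open-label and is not affected.

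**Working it through.** There is no figure in the plan to reproduce. The check compares the sections, then works out what one envelope reveals.

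**1. Is it the same event?** Protocol 9.1.3 does not define its scheduled safety reviews. The only ones described for Part I are the sentinel and cohort reviews in 14.5, and both are DRSC reviews under 15.2. So it is the same event.

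**2. Side by side, for a DRSC review in Part I**

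| Question | Protocol 9.1.3 | Protocol 15.2 |
|---|---|---|
| Who may see the allocation? | The Investigator, by opening an envelope | "the DRSC may choose to unblind the data to the Sponsor only" |
| Status of the Investigator | Blinded, but allowed to open an envelope if warranted | "Every effort will be maintained to keep the Investigator blinded" |
| Force of the text | Permissive | Permissive on unblinding; best efforts on the Investigator |

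The emergency and medical-safety occasions in 9.1.3 are compatible with a best-efforts aim. The scheduled-review occasion is not, because 15.2 already provides a Sponsor-only route for that purpose.

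**3. What one envelope reveals.** Inputs: sentinel pair 1 active and 1 placebo; remaining six 5 active and 1 placebo (Protocol 4.1). The block composition is stated in the protocol, so the Investigator is assumed to know it.

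- Sentinel pair: one envelope fixes both allocations, 2 of 2.
- Remaining six, envelope picked at random: it is the placebo with probability 1/6, and then all 6 are known. With probability 5/6 it is an active, and then only that subject is known; each of the other five moves from a 5/6 to a 4/5 probability of active.
- Expected number known in the six: (1/6 × 6) + (5/6 × 1) = 11/6, about 1.83.

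An envelope opened because of an event would not be picked at random, so 1/6 is a reference value only.

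**4. Ceiling on opportunities.** Up to 9 planned cohorts × 2 reviews = up to 18. This counts meetings at which the clause could be invoked.

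**5. Which judgements could follow an unblinding?** In the Part I schedule of events, AE assessments after dosing fall on Days 1, 2, 3, 4 and 11/EOS. The sentinel review uses 24 hours of data and the cohort review uses data up to 72 hours. After Day 4, the only scheduled AE assessment is Day 11/EOS. Protocol 10.1.1 also follows ongoing AEs to resolution or 14 days after EOS/ET, and 10.1.3 lets the Investigator revise the causality of an SAE on follow-up information. Some judgements can therefore come after an unblinding, while events already rated were rated blind.

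**6. Weight of one rating.** One subject reclassified as having, or not having, a related TEAE moves an active cohort by 1/6 = 16.7 percentage points. With all nine cohorts enrolled, the pooled placebo group is 9 × 2 = 18, and one subject moves it by 1/18 = 5.6 points.

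**The case against.** The strongest case on the other side has five parts.

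- **Both texts are permissive.** Protocol 9.1.3 applies only if unblinding is warranted, and 15.2 states an aim for the Investigator and not a bar. A reader might infer that 15.2 forbids what 9.1.3 allows, or that following 9.1.3 necessarily unblinds the AE assessor. Neither is supported: a site can comply with 9.1.3 and never open an envelope at a review. The mismatch over who may see the allocation remains.
- **Controls exist.** Non-emergency requests for randomization information need a disclosure form, the Medical Monitor is contacted within 24 hours of a disclosure, each disclosure is filed at site, the Sponsor is told, and suspected unblinding must not be passed to blinded team members. These controls record and contain a disclosure; they do not withdraw the permission.
- **The assessor may be someone else.** A sub-Investigator could rate causality and stay blinded. That would work, but no visible text requires it.
- **The effect on the analysis is limited.** TEAE summaries are descriptive, and only later ratings of opened or deducible subjects are exposed. Intensity of laboratory and vital-sign AEs is graded on the scale in Appendix 6, which leaves less room for judgement. All this stands, and it makes the bias conditional and partial.
- **Some text cannot be read.** The stopping criteria in Protocol 6.4 are not visible, and SAP 3.4 may be incomplete. Either might say more about unblinding.

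A reader might also want to turn the 24-hour and 72-hour marks into a share of study days assessed unblinded. The documents give no meeting dates, and calendar days are not assessments, so no such figure can be supported.

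**Conclusion.** The inconsistency is real and confined to one clause in Part I. At a scheduled DRSC review, 9.1.3 permits disclosure to the person whom 15.2 seeks to keep blinded, and the legible SAP does not resolve it.

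The consequence is conditional. If the clause is used, the person who rates AE severity and relationship, or who delegates that rating, could know the allocation before later judgements are made. This can bias those two components of the primary endpoint for the opened subject and anyone deducible from it. It is not shown that bias will occur. The figure of 18 reviews and the disclosure of all six subjects are upper bounds.

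The conclusion assumes that the scheduled safety reviews in 9.1.3 are the DRSC reviews of 14.5, and that nothing in the hidden text closes the gap. Confidence is high on the textual conflict and lower on how often it would matter. The change should be made because it is cheap and protects the primary endpoint.

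**What to change.** Reconcile 9.1.3 with 15.2:

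- In 9.1.3, remove the scheduled-review clause from the Investigator's permitted uses of the envelopes. Leave emergency and subject-safety unblinding exactly as they are.
- In 15.2, state that any unblinding requested at a DRSC review goes from the unblinded pharmacist or unblinded statistician to a designated Sponsor role, without disclosure to the Investigator, and that the Investigator leaves any unblinded part of the discussion.
- Check that the stopping criteria in 6.4 and the full text of SAP 3.4 agree with this route.

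The cost is about one sentence in each of 9.1.3 and 15.2. No new staff are needed, since both unblinded roles already appear in 9.1.3. The downside is small but should be acknowledged: the Investigator, one of the three named DRSC members, is absent from any unblinded part of a review.
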